### **11.1 Proven invasive pulmonary aspergillosis**

Microscopic analysis on sterile material: histopathologic, cytopathologic, or direct microscopic examination of a specimen obtained by needle aspiration or sterile biopsy in which hyphae are seen accompanied by evidence of associated tissue damage. Culture on sterile material: recovery of *Aspergillus* by culture of a specimen obtained by lung biopsy.

### **11.2 Probable invasive pulmonary aspergillosis (fulfil both clinical, radiological and mycological criteria)**

**Clinical criteria:** One of the following signs or symptoms must be present:

- Fever refractory to at least 3 days of appropriate antibiotic therapy.
- Recrudescence fever after a period of defervescence of at least 48 h while still on antibiotics and without other apparent cause
- Dyspnea
- Hemoptysis
- Pleural friction rubs or chest pain

**Radiological criteria:**

Any infiltrate on pulmonary imaging by portable chest x-ray or CT-scan of the lungs.

**Mycological criteria:** One of the following findings:

- Positive microscopy or culture of *Aspergillus* from BAL
- Galactomannan optical index on BAL >0,8
- Galactomannan optical index on serum  $\geq 0,5$

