### 3. PROTOCOL SUMMARY

- Title:** Prevalence of Influenza Related Invasive Aspergillosis; A Multicenter Prospective Observational Cohort Study
- Overview:** A multicenter prospective observational study conducted at 12 intensive care units in Sweden. All patients >18 years of age with a PCR-verified influenza A or B diagnosed up to 7 days before admission to the ICU or during ICU care, will be included in the study. A new clinical routine will be implemented: During the ICU stay screening with Beta-D-glucan and Galactomannan in blood/serum will be performed twice weekly and a respiratory sample will be retrieved for fungal culture and microscopy once weekly. All results from collected samples will be available to the patient responsible physicians. Clinical and microbiological data will be collected, and the diagnosis of invasive aspergillosis will be made using predefined diagnostic criteria.
- Objectives:**
1. To determine the prevalence of influenza-related invasive pulmonary aspergillosis in Swedish intensive care units
  2. To assess the clinical impact of and risk factors for influenzarelated invasive pulmonary aspergillosis
- Population:**  $\geq 18$  years of age. Confirmed influenza A or B diagnosed <7 days before admission to the ICU or during ICU stay. At least 50 patients will be enrolled in the study.
- Number of sites:** 12
- Study duration:** 1 year
- Enrolment:** Until the end of April 2020 if  $\geq 50$  patients have been enrolled. Enrolment will continue until  $\geq 50$  patients have been recruited.

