### **7.2 Study inclusion**

At least 50 patients will be enrolled in the study. The target sample size has been calculated using the expected prevalence of 15% IPA. The sample size is then sufficient to describe the prevalence with 10 % margin of error at the 95% confidence level. Approximately 100 influenza patients are admitted to ICUs of the participating centers every influenza season.

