## **11 STUDY ENDPOINTS**

Enrolled patients will be categorized as proven or probable IPA at discharge from the ICU to answer the primary objective of evaluating the prevalence of influenza related invasive pulmonary aspergillosis. A modified version of the Asp-ICU criteria will be used, described below 11.1, 11.2.

All recorded baseline characteristics will be compared between patients diagnosed with IPA and those that were not. The following outcome parameters will also be assessed: SOFA-score, use of mechanical ventilation, use of non-invasive ventilation, use of vasopressor, use of renal replacement therapy, ARDS-grade using the Berlin definition, median number of ICU stay, ICU mortality, and 90-day mortality after ICU admission.

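### ICU stay and mortality are compared by an IPA status that a longer stay makes easier to acquire, and the share of cases resting on a single serum galactomannan will not be visible

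*Combined protocol and SAP*

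**What the plan says.** - **Testing.** The protocol summary (Section 3) states that "screening with Beta-D-glucan and Galactomannan in blood/serum will be performed twice weekly". Section 7.1 adds that no sampling is compulsory under the protocol.
- **Case definition.** Probable IPA (Section 11.2) needs a clinical, a radiological and a mycological criterion together. The clinical one is met by any of five signs, dyspnoea included. The radiological one is "Any infiltrate on pulmonary imaging by portable chest x-ray or CT-scan of the lungs". For mycology, "One of the following findings" is enough, and the list includes "Galactomannan optical index on serum" at 0.5 or above. No repeat or confirmatory test is asked for.
- **Timing of status.** Section 11 classifies patients at discharge from the ICU.
- **Comparison.** Section 11 then compares outcomes by that status, including "median number of ICU stay, ICU mortality, and 90-day mortality after ICU admission". Section 12 plans two-group tests and a survival analysis. It mentions no adjustment for the number of tests, no time-dependent status, no breakdown by qualifying criterion and no sensitivity estimate of prevalence.
- **Precision.** Section 7.2 says "At least 50 patients will be enrolled in the study", from an "expected prevalence of 15% IPA" and a "10 % margin of error at the 95% confidence level".

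**The concern.** A patient who stays three days may be tested once; one who stays four weeks may be tested eight times. Each test is another chance to cross the threshold, whether because a true infection is finally picked up or because of a false positive. Group membership therefore depends in part on length of stay, and length of stay is then compared between the groups. Some difference is built in.

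The survival comparison has the same structure. Time runs from ICU admission, but status is fixed later, so a patient who dies before a positive sample falls into the comparison group by default.

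For the primary estimate, the clinical and radiological criteria are wide enough that the mycological result will plausibly decide many cases. Section 5.2 says that a prevalence close to published reports should lead to national guidelines. A reader of the result would want to know how many cases rest on one serum value, and the plan does not provide for that.

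**Working it through.** **The plan's own figure.** n = 1.96² × 0.15 × 0.85 / 0.10² = 48.98, so 49 against the stated 50. It reproduces. The half-width at n = 50 is 1.96 × √(0.15 × 0.85 / 50) = 9.9 points. The calculation takes case status as error-free.

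**Inputs.** From the documents: two serum tests a week, any one positive suffices, status set at discharge, 15% expected prevalence, at least 50 patients, and about 100 influenza admissions a season at the participating ICUs (Section 7.2). Not in the documents and therefore assumed: per-test specificity 0.95–0.99, sensitivity 0.25–0.60, the distribution of stay, and independence of errors between tests unless stated. Only the serum route is modelled, and the clinical and radiological criteria are taken as met unless stated.

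**Step 1. Chance of at least one false positive in k tests:** 1 − specificity^k.

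| Specificity | k = 1 | k = 2 | k = 4 | k = 8 |
|---|---|---|---|---|
| 0.99 | 1.0% | 2.0% | 3.9% | 7.7% |
| 0.98 | 2.0% | 4.0% | 7.8% | 14.9% |
| 0.95 | 5.0% | 9.8% | 18.5% | 33.7% |

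The k = 8 column concerns few patients. In the stay model of Step 2 the median is 3 tests, about 35% have 4 or more, and about 7% have 8 or more.

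**Step 2. No true IPA.** Stay = 1 day + exponential with mean 9 days; tests = floor(stay / 3.5) + 1. At specificity 0.99, 0.98 and 0.95 the mycological criterion is met in about 3.3%, 6.4% and 15% of patients. Median stay is about 13–14 days in those labelled positive and about 7 in the rest. A Mann–Whitney test at P < 0.05 then rejects in about 20% of studies of 50 patients at specificity 0.98 and 42% at 0.95; with 100 patients, about 38% and 72%. The nominal rate is 5%.

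**Step 3. True IPA in 15%, unrelated to stay.** Here stay is log-normal with median 7 days and log-SD 0.9.

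| Specificity / sensitivity | Counted prevalence | False share of cases | Median stay, counted IPA vs others |
|---|---|---|---|
| 0.95 / 0.40 | 23.7% | 56% | 11.0 vs 6.2 days |
| 0.98 / 0.25 | 13.7% | 41% | 11.4 vs 6.5 days |
| 0.99 / 0.60 | 15.7% | 18% | 8.9 vs 6.7 days |
| 1.00 / 0.40 | 10.6% | 0% | 9.0 vs 6.8 days |

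The last row has no false positives and the gap remains, because true cases also get more chances of detection in a longer stay. Under the stay model of Step 2 the same row gives 9.6 vs 7.0 days.

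**Step 4. Weaker assumptions.** With false positives correlated within patients (beta-binomial, correlation 0.3), no true IPA, specificity 0.95 and the log-normal stay, the positive share falls from 15.4% to 10.5% and the gap from 12.8 vs 6.3 to 10.4 vs 6.7 days. If only 60% of IPA-free patients meet the clinical and radiological criteria, the first row of Step 3 counts 18.4% instead of 23.7%. The gap persists in every scenario run.

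**Step 5. Would a stricter count rule help?** Requiring two positive sera in the first row of Step 3 cuts the false share from 56% to 22%, but counted prevalence falls to 6.6% and the gap widens to 16.4 vs 6.6 days. Changing the definition does not cure the stay comparison.

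**The case against.** Several counter-arguments have force.

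- *A positive serum does not by itself make a case.* Correct: a clinical sign and an infiltrate are also required. How many patients meet both is not given; that most would is plausible but not documented.
- *The prevalence is not shown to be inflated.* Also correct. A reader might infer from Step 1 that the estimate must be too high. It need not be, because missed cases pull the other way. Over specificity 0.95–0.99 and sensitivity 0.25–0.60, the count under the exponential stay model runs from 10.9% to 25.6% against a true 15%, and BAL findings are left out. At specificity 0.99 with no true IPA the excess is 3.3% of 50, fewer than 2 patients, against a 10-point margin.
- *False positives are blamed for the stay gap.* A reader might infer this too. The gap at perfect specificity shows that they add to it but are not its root.
- *Testing may be less frequent than twice weekly.* True, since sampling is not compulsory. This lowers the number of tests. It does not break the link between tests and stay, and it is a reason to report tests per patient.
- *Severity is biased as well.* This was not calculated. SAPS3 and SOFA on arrival, and organ support at enrolment (Section 9.1), are recorded at fixed early points, so the claim should not be extended to them.
- *Much can be reconstructed already.* Partly so. Section 9.1 records the type of microbiological finding and plans a record review, but it lists no test dates, index values or test counts.

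None of this answers the central point that status fixed at discharge is used to compare time spent before discharge.

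**Conclusion.** The concern holds for the outcome comparisons and, in limited form, for the prevalence.

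- **ICU stay.** The planned crude comparison is biased towards a longer stay in the IPA group, with no IPA effect and even with no false positives. Illustrative size: 13–14 vs 7 days with no true IPA; 9.6 vs 7.0 days at specificity 1.0 and sensitivity 0.40. The direction was the same under both stay models and with correlated errors. The size depends on assumed inputs. The gap would vanish only if the number of tests had no bearing on who is classified.
- **Mortality.** The need to survive to a positive sample follows from the design. Its size was not calculated.
- **Prevalence.** An unknown share of counted cases may be false: 18–56% in the Step 3 rows with imperfect specificity. The documents do not support saying which way the total is off.

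This is an improvement to the analysis plan. It is not a reason to change the case definition or the sample size.

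**What to change.** Keep the case definition. Add to Section 12:

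1. A table of cases by qualifying basis (proven; BAL culture or microscopy; BAL galactomannan; two or more positive sera; single serum only), with the number of galactomannan tests per patient.
2. A sensitivity prevalence that leaves out cases resting on a single serum value. Label it a lower-side estimate, because it may also drop true cases whose stay was too short for a second sample.
3. For ICU stay and mortality, IPA status treated as time-dependent from the date of the qualifying sample, or a landmark analysis with the landmark day fixed in advance. Present the crude difference in stay as descriptive only.

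Record the date and index of each galactomannan test; the record review planned in Section 9.1 could supply them.

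**Cost:** a little more data entry and analysis, a second prevalence figure below the primary one, and imprecise time-dependent estimates. At 15% of 50 patients, about 7 or 8 cases are expected (0.15 × 50 = 7.5), so item 3 will guard against a misleading reading more than it will give a firm effect estimate.

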## **12 STATISTICAL ANALYSIS**

Prevalence of Proven/Probable IPA will be calculated at the 95% confidence level. Patients meeting the criteria for proven/probable IPA will be compared to the influenza positive patients who do not meet the criteria, in terms of underlying risk factors and outcome measures. Categorical variables will be assessed by Fischer exact test and  $X^2$  test, and continuous variables with t-test or Mann Whitney U test where appropriate. We will also perform multivariable analysis by binary logistic regression to detect independent risk factors for IPA. All analyses will be conducted using a threshold of 95% confidence level (P-value 0.05). ICU mortality and 90 days after admission to the ICU mortality will be compared using survival analysis.

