### **6.2 Secondary objective**

To assess the clinical impact and risk factors related to influenza-related invasive pulmonary aspergillosis. Patients with proven or probable IPA will be compared to patients that do not meet the criteria for proven and probable IPA. Baseline characteristics and clinical data such as SAPS3, SOFA score, need for invasive ventilation and need for continuous renal replacement therapy, will be assessed to find risk factors for IPA.

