## **7. STUDY DESIGN**

### **7.1 Study overview**

The study is a Swedish, nationwide, multicenter, prospective observational cohort study to determine the prevalence of IPA among patients admitted to the ICU with confirmed influenza infection.

A new clinical routine regarding IPA-testing will be implemented at the participating centers, similar to the current guidelines in the Netherlands. All samples will be retrieved and analyzed using local methods and logistics. All test results will be available to the patient responsible physician, who is free to act on them as deemed appropriate.

The study is non-interventional, no measurements or sampling will be made mandatory by the protocol and data collection at these pre-specified time-points will only take place if decided acceptable by the patient responsible physician. All aspergillus testing is part of the new clinical routine, and no additional sampling will be performed on accounts of the study.

All patients  $\geq 18$  years of age with confirmed influenza A or B diagnosed up to 7 days before ICU admission, or during ICU care, will be included in the study. Patient consent was waived in the ethics approval from *the Swedish Ethical Review Authority* (Dnr 201900557).

Recruitment is planned to begin in December 2019. Recruitment of patients is expected to stop in April 2020 if  $\geq 50$  patients have been recruited, or after that when 50 patients have been recruited.

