### **7.3 Inclusion criteria**

Patients must meet all the inclusion criteria to be eligible for the study:  $\geq 18$  years of age, PCR-verified influenza A or B diagnosed within 7 days of ICU admission, or during ICU stay.

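### Does Section 12 leave the prevalence denominator, and the handling of patients without a usable Aspergillus test, undefined?

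*Combined protocol and SAP*

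**What the plan says.** For the primary estimate, Section 12 says only this: "Prevalence of Proven/Probable IPA will be calculated at the 95% confidence level". On the comparison it says "Patients meeting the criteria for proven/probable IPA will be compared to the influenza positive patients who do not meet the criteria", and Section 6.2 says the same: "Patients with proven or probable IPA will be compared to patients that do not meet the criteria for proven and probable IPA". Neither makes membership of the comparator conditional on having been tested.

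Section 11 describes the classification: "Enrolled patients will be categorized as proven or probable IPA at discharge from the ICU". The same sentence goes on to say that this is done to answer the primary objective. Section 7.1 defines the target as IPA prevalence among ICU patients with confirmed influenza and includes all such adults. Section 7.2 bases the sample size for that prevalence on at least 50 enrolled patients.

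On testing, Section 7.1 states that "no measurements or sampling will be made mandatory by the protocol" and that "data collection at these pre-specified time-points will only take place if decided acceptable by the patient responsible physician". It also says that all Aspergillus testing belongs to the new clinical routine. Section 3 describes that routine: Beta-D-glucan and galactomannan in blood or serum twice a week, and a respiratory sample once a week. Under Section 11.2, probable IPA needs a mycological finding from BAL or serum galactomannan. Under Section 11.1, proven IPA needs a lung biopsy culture or "examination of a specimen obtained by needle aspiration or sterile biopsy".

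**The concern.** Entry and case status rest on different things. Section 7.3 says "Patients must meet all the inclusion criteria to be eligible for the study", and those criteria are age and PCR-verified influenza, with nothing about Aspergillus testing. Case status needs a qualifying result. Beta-D-glucan is not among the mycological criteria, and the weekly respiratory sample is not specified as BAL. A patient without BAL or tissue can therefore become a case only through serum galactomannan.

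A patient with no qualifying result is thus a non-case whatever the truth. Section 5.2 itself argues that IPA can be missed unless it is specifically looked for, so such a patient is better described as unknown than as negative. Counting unknowns as negatives can lower the primary prevalence and place missed cases in the comparator for the risk-factor and mortality analyses. Section 12 has no evaluable set, no unclassifiable category and no sensitivity analysis. The prevalence is meant to inform national testing guidance, so it is reasonable to ask whether this matters.

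**Working it through.** **1. Reproduce the plan's sample size.** Inputs from Section 7.2: expected prevalence p = 0.15, margin d = 0.10, 95% confidence.

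n = 1.96² × p(1 − p) / d² = 3.8416 × 0.1275 / 0.01 = 48.98, rounded up to 49. The plan's 50 agrees. The half-width at 50 is 1.96 × √(0.1275/50) = 9.9 points. The calculation treats all 50 enrolled patients as the denominator.

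**2. Is the denominator really open?**
- Section 7.1: the target is prevalence among ICU patients with confirmed influenza, all of whom are included.
- Section 7.2: precision is computed on enrolled patients.
- Section 11: enrolled patients are classified in order to answer the primary objective.
- Sections 6.2 and 12: whoever does not meet the criteria is in the comparator.

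All-enrolled is the only denominator these sections support. Section 12 does not repeat it.

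**3. Who would lack a qualifying result?** Section 3 pairs Beta-D-glucan with galactomannan, twice weekly. A patient with Beta-D-glucan alone, or with only a non-BAL respiratory sample, has departed from the routine. The patients left are those the routine missed, or who died or left the ICU before the first sample.

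**4. Size of the effect.** The documents give no testing rate. Let u be the share without a qualifying result, assumed to be 5%, 10% or 20%. Assume perfect tests and the same 15% prevalence in that group.
- Reported prevalence = 0.15 × (1 − u)
- Missed cases per 50 enrolled = 50 × 0.15 × u
- Missed share of the comparator = 0.15u / (1 − 0.15(1 − u))

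| u | Reported prevalence | Shift (points) | Missed per 50 | Share of comparator |
|---|---|---|---|---|
| 5% | 14.25% | 0.75 | 0.375 | 0.0075/0.8575 = 0.9% |
| 10% | 13.5% | 1.5 | 0.75 | 0.015/0.865 = 1.7% |
| 20% | 12.0% | 3.0 | 1.5 | 0.030/0.880 = 3.4% |

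**5. Would an evaluable-only figure be better?** If the untested patients truly had no IPA, the all-enrolled figure stays at 15%. The evaluable-only figure would then be too high: 0.15/0.95 = 15.8%, 0.15/0.90 = 16.7%, 0.15/0.80 = 18.8%. It is also less precise. The half-width is 1.96 × √(0.1275/45) = 10.4 points with 45 evaluable and 1.96 × √(0.1275/40) = 11.1 with 40.

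As an example with assumed counts, take 6 cases in 50 with 5 non-evaluable. All-enrolled gives 12.0% (Wilson 95% interval 5.6 to 23.8) and evaluable-only gives 6/45 = 13.3% (6.3 to 26.2). The two intervals largely overlap.

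**6. Would removing untested patients improve the comparison?** A case always has a qualifying result, so exclusion removes patients from the comparator only. With assumed counts of 8 deaths in 39 evaluable non-cases (20.5%) and 5 non-evaluable patients, comparator mortality with the 5 kept is 13/44 = 29.5% if all 5 die and 8/44 = 18.2% if all 5 live. Removing them therefore lowers it by 9.0 points or raises it by 2.3. The direction depends on who was not tested, and early deaths are plausible candidates.

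**The case for a change.** The strongest argument for changing the text is that sampling error shows in the confidence interval, whereas uncertainty from untested patients would not show anywhere. A reader given x out of 50 cannot judge it without knowing how many of the 50 could have been classified. A planned routine does not guarantee a result, least of all in short stays or early deaths. The remedy looks cheap: one sentence on the denominator and one table of testing coverage, drawn from the record review already planned in Section 9.1. If coverage proved high, the table would strengthen the result.

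Part of this stands. No section promises a coverage table or an evaluable-only estimate, and a good report would say how many patients had BAL, serum galactomannan only, or neither. Nothing in the plan prevents that. Section 9.1 has microbiological findings reviewed in the records, and Section 10 has missing data queried. The CRF and the workflow figure, which might show how tests not done are recorded, are not in the text available here.

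The claim that the denominator and the handling rule are absent does not stand. Stating them would restate what Sections 6.2, 7.1, 7.2, 11 and 12 already yield together. The additional analyses bring biases of their own: evaluable-only prevalence is too high if physicians test on suspicion, and exclusion from the comparator alone can move the mortality contrast either way.

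**Conclusion.** The concern does not call for a change. Section 12 is terse, but the rest of the protocol fixes all enrolled patients as the denominator and counts those who do not meet the criteria as non-cases. An analyst following the document would produce that figure, and it is also the figure a clarified text would ask for.

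On assumed rates of 5% to 20% without a qualifying result, the possible understatement is 0.75 to 3.0 points, or about 0.4 to 1.5 cases per 50, against a planned margin of 10 points. This rests on perfect tests and on equal true prevalence in tested and untested patients. If the untested had no IPA, the planned figure has no bias from this source. With twice-weekly serum galactomannan in the routine, the lower rates are more plausible, although the documents give no testing rate to confirm it. The documents do not show that the planned estimate is wrong. What remains is a matter of reporting, which the investigators can meet in the paper with data they already plan to review.

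### ICU stay is tested between groups defined by IPA status at ICU discharge, which favours a longer stay in the IPA group even with no IPA effect; the ICU-mortality method is under-specified

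*Combined protocol and SAP*

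**What the plan says.** The secondary objective is "To assess the clinical impact and risk factors related to influenza-related invasive pulmonary aspergillosis" (Section 6.2). Section 11 fixes the grouping: "Enrolled patients will be categorized as proven or probable IPA at discharge from the ICU". Testing is repeated until then: "During the ICU stay screening with Beta-D-glucan and Galactomannan in blood/serum will be performed twice weekly" (Section 3), with a weekly respiratory sample. Under Section 11.2 a single qualifying mycological finding meets that criterion, and no time window is set. Section 7.1 adds that "no measurements or sampling will be made mandatory by the protocol", so actual test times may differ between patients.

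The outcomes in Section 11 include "median number of ICU stay, ICU mortality, and 90-day mortality after ICU admission". Section 12 compares the two final groups: "Patients meeting the criteria for proven/probable IPA will be compared to the influenza positive patients who do not meet the criteria", testing "continuous variables with t-test or Mann Whitney U test where appropriate". On mortality it says only "ICU mortality and 90 days after admission to the ICU mortality will be compared using survival analysis". Section 9.1 follows survival to 90 days from ICU admission and collects the discharge destination. No section gives a landmark, an IPA onset date or a time-dependent IPA status.

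**The concern.** For ICU stay, the group label depends partly on the outcome. A patient who leaves or dies on day 2 has had one or two chances to test positive; a patient who stays three weeks has had many. Unless cases are already positive on arrival, the IPA group is enriched for long stays whatever IPA does. The named tests treat the label as if it were known at admission.

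For ICU mortality, two choices that drive the answer are left open: when a patient starts to count as IPA, and what happens to patients discharged alive.

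At stake is the clinical-impact half of the secondary objective. A spurious p-value for ICU stay could be read as evidence that IPA prolongs intensive care.

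**Working it through.** **Plan's own figure.** Section 7.2: 15% prevalence, 10-point margin, 95% confidence. n = 1.96² × 0.15 × 0.85 / 0.10² = 48.98, so 49 against the stated minimum of 50. This reproduces. Expected IPA cases: 0.15 × 50 = 7.5.

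**Inputs from the documents.** Prevalence 15%; n = 50, or about 100 in one season (Section 7.2); alpha 0.05 (Section 12), taken as two-sided.

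**Assumptions (not in the documents).** IPA has no effect. Daily ICU death/discharge hazards: A 0.025/0.08; B 0.03/0.05; C 0.05/0.03 to day 4, then 0.02/0.09; D 0.015/0.12 to day 5, then 0.035/0.05. Death hazard after discharge 0.002 per day. A share s of cases is positive at admission. The rest are detected at a constant rate, either through the whole stay or only in the first 7 days, tuned to 15% ever IPA.

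**Closed form for mean stay (constant hazards, detection throughout).** Let p = 0.15 and q = (1−s)p/(1−sp), the chance that a patient negative at admission is detected before leaving. In units of 1/(total exit hazard), mean stay is 2−q for late-detected cases, 1 for cases positive at admission and 1−q for non-IPA patients. The IPA to non-IPA ratio is [s + (1−s)(2−q)]/(1−q); the exit hazard cancels.

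- s = 0: q = 0.150; 1.850/0.850 = 2.18
- s = 0.5: q = 0.0811; 1.459/0.919 = 1.59
- s = 0.8: q = 0.0341; 1.193/0.966 = 1.24
- s = 1: ratio 1.00

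At a total exit hazard of 0.105 per day and s = 0.5 this is 1.459/0.105 = 13.9 against 0.919/0.105 = 8.8 days, with no IPA effect.

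**Simulated false positives for ICU stay (ranges over sets A to D).** The 0% column is an extreme case.

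| Test and detection pattern | 0% at admission | 50% | 80% | 100% |
|---|---|---|---|---|
| Mann-Whitney, n=50, throughout | 60-80% | 20-29% | 7-8% | 5-6% |
| Mann-Whitney, n=100, throughout | 90-98% | 39-50% | 10-12% | 4-5% |
| t-test, n=50, throughout | 61-79% | 27-35% | 10-14% | 5-6% |
| Mann-Whitney, n=50, first 7 days only | 14-31% | 7-11% | 4-6% | not applicable |

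A second model (log-normal stay with median 5, 7 or 10 days, a test every 3.5 days) gave similar n=50 Mann-Whitney rates: 21-31% at 50% and 8-10% at 80%.

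**ICU death.** If the analyst fixes groups from admission and censors live discharge, the null hazard ratio is 0.60-0.62 at 50% and 0.79-0.82 at 80% (detection throughout), so IPA looks protective. The handling of live discharge also matters by itself. Under set A, the day-28 ICU death estimate with discharge censored is 1 − exp(−0.025 × 28) = 50%; the cumulative incidence is (0.025/0.105) × (1 − exp(−0.105 × 28)) = 23%.

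**90-day death, fixed groups.** Log-rank false positives are 3-9% at n=50 and 3-11% at n=100. The null hazard ratio ranges over 0.79-1.12 at 50% and 0.89-1.07 at 80%.

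**Check of the remedy.** With IPA switched on at detection, the null ICU-death hazard ratio is 0.97-1.02, and type I error in the second model is 0.045-0.065.

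For 90-day death, switching alone is not enough, because detection happens only in the ICU and detected patients are more often still there. Take set A, s = 0.5: detection rate 0.105 × 0.0811/0.9189 = 0.00927 per day. At day 7, per patient admitted:

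- All patients: in ICU e^(−0.735) = 0.480; discharged alive 0.08 × (e^(−0.014) − e^(−0.735))/0.103 = 0.393.
- Undetected: in ICU 0.925 × e^(−0.800) = 0.416; discharged alive 0.925 × 0.08 × (e^(−0.014) − e^(−0.800))/0.1123 = 0.354.
- IPA, by subtraction: 0.064 and 0.040.

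So 61.6% of IPA and 54.0% of undetected patients are in the ICU. Average death hazards are 0.616 × 0.025 + 0.384 × 0.002 = 0.0162 and 0.540 × 0.025 + 0.460 × 0.002 = 0.0144, a ratio of 1.12 with no IPA effect. Within the ICU, and within the discharged, the hazards are equal by construction, so stratifying on current ICU status removes this.

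**The case against.** The strongest reply is that the size is unknown and could be small. Routine testing is introduced to find IPA early (Section 5.2). If late cases all appear in the first week, 80% positive at admission already gives nominal error, and 50% gives only 7-11%. That stands. A reader might infer that the ICU-stay test is badly inflated unless nearly all cases are positive on arrival. The documents do not support that, because it also needs detection to continue late into the stay, and they say nothing on detection times. An early-testing aim does not establish early detection either.

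A reader might also infer that 90-day mortality lacks a time origin or a discharge rule. It does not: it runs from ICU admission, survival is followed past discharge, and its false-positive rate stays close to nominal. The live-discharge gap concerns ICU mortality only. The protective hazard ratio of about 0.6 comes from one possible reading of an unspecified method, so it is not an error written into the plan. With hazards that change over the stay, crude ICU mortality can be off in either direction; with constant hazards it differs by at most 1 point.

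Nor can one conclude that sample dates go uncollected. Section 9.1 lists the findings without a date, but the CRF itself is not in the documents, and microbiology records are reviewed.

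None of this supplies a rule for when IPA status begins.

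**Conclusion.** The point holds for ICU stay. The direction of the bias follows from the design; its size does not. Under the stated hazards and 15% prevalence, false positives at n=50 run from nominal (all cases positive at admission) through 7-11% (half positive, the rest found within 7 days) to 20-29% (half positive, detection throughout). They rise with sample size. For ICU mortality the fault is under-specification. For 90-day mortality the effect on error rates is small, although fixed groups can still shift the hazard ratio. The prevalence estimate and its sample size are unaffected. This should be fixed before analysis, but it does not threaten the primary objective.

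**What to change.** In Section 12:

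1. Report ICU stay by final IPA status as description only, without a p-value.
2. For ICU death, use a cause-specific hazard model with entry at enrolment and IPA as a time-dependent status that switches on at the collection date of the first qualifying sample. Report cumulative incidence with live discharge as a competing event.
3. For 90-day death, use the same time-dependent status and stratify by whether the patient is currently in the ICU or discharged, for the reason shown above. This removes any part of an IPA effect that acts through a longer stay, so state it as a limitation. As an optional sensitivity analysis, use a landmark with a pre-stated day counted from ICU admission, limited to patients enrolled and still in the ICU on that day. The enrolment condition is needed because influenza may be diagnosed during the ICU stay.
4. Confirm that the sample collection date is captured. If not, recover it in the record review already planned in Section 9.1.

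The cost is analysis wording and at most one added date. The downside is precision. With 7-8 expected IPA cases among 50 patients, estimates will be wide, and a landmark keeps fewer cases and counts later ones as non-IPA. Give confidence intervals and read the results as descriptive.
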